5.3.2. Safety Evaluable Population

The safety evaluable population includes all participants who received at least 1 dose of study drug. All safety and exposure analyses will be conducted using the safety evaluable population. In this study, the FAS and safety evaluable population are identical.

5.3.3. Pharmacokinetic Evaluable Population

The PK evaluable population will include all participants who received at least 1 dose of study drug and have provided a baseline and at least 1 postdose PK sample.

6. BASELINE, EXPOSURE, AND DISPOSITION VARIABLES AND ANALYSES

Appendix A provides a list of planned tables, figures, and listings.

6.1. Baseline and Demographics, Physical Characteristics, and Disease History

Baseline disease characteristics and demographics will be summarized by disease-specific cohort. Overall summaries combining 4 tumor-specific cohorts will be presented.

6.1.1. Demographics

Demographics will be listed in detail. The following demographics will be summarized for the FAS by disease-specific cohort and overall FAS: age, sex, race, ethnicity, body weight, height, BMI, and creatinine clearance. Qualitative data will be summarized by contingency table while quantitative data will be summarized by descriptive summary statistics.

6.1.2. Baseline Disease Characteristics and Cancer History

According to data collected in the eCRF, the following information determined at initial diagnosis and baseline will be summarized for in the FAS by disease-specific cohort:

- Melanoma: time since initial diagnosis, time since unresectable/metastatic diagnosis, stage at baseline, classification M at baseline, histology at baseline, sites of disease at baseline, BRAF status, PD-L1 status, and ECOG performance status at baseline.
- NSCLC: time since initial diagnosis, time since metastatic diagnosis, histopathology at initial diagnosis, stage at baseline, T staging at baseline, N staging at baseline, M staging at baseline, sites of disease at baseline, PD-L1 status, EGFR mutation, ALK re-arrangement status, ROS1 re-arrangement status, and ECOG performance status at baseline.
- Urothelial cancer (bladder cancer): time since initial diagnosis, time since advanced/metastatic diagnosis, cancer type at initial diagnosis, histology at initial diagnosis, reason for cisplatin ineligibility at initial diagnosis, TNM classification T at baseline, TNM classification N at baseline, TNM classification M at baseline, grade at baseline, histology at baseline, sites of disease at baseline, stage at baseline, PD-L1 status, and ECOG performance status at baseline.
- RCC: time since initial diagnosis, time since advanced/metastatic diagnosis, histology at initial diagnosis, MSKCC criteria at initial diagnosis, stage of disease at baseline, TNM classification T at baseline, TNM classification N at baseline, TNM classification M at baseline, sites of disease at baseline, PD-L1 status, and ECOG performance status at baseline.

Additional baseline disease characteristics and cancer history for individual cancer types listed in eCRF may be summarized or listed for all participants by tumor type specific cohort. Time since initial diagnosis (advanced/ unresectable /metastatic diagnosis) will be calculated as follows:

Time since initial diagnosis (months) = (Day 1 date – date of diagnosis + 1) / 30.4375.

6.1.3. Prior Therapy

The number and percentage of participants recording any prior systemic cancer therapy, prior radiotherapy, or prior surgery will be summarized. The component drugs of prior systemic therapy regimens will be coded using the WHO Drug Dictionary. Lines of prior systemic cancer therapy will be summarized by disease-specific cohort. Best response from prior therapy, purpose, reason for discontinuation, as well as time to progression on prior therapy will be summarized and listed wherever the data are available.

Number of participants who received prior radiotherapy will be listed for the FAS. Anatomical location of the administration, start and stop date, reason for regimen, best response, number of fractions received and total dose will be listed.

Number of participants who had prior surgery or surgical procedure for cancer treatment will be listed for the FAS. Date and description of the surgery/surgical procedure will be listed. Detailed information on prior systemic cancer therapy, prior radiation, and prior surgery will be listed in 3 separate listings.

6.1.4. Medical History

For all participants in the FAS, medical history will be summarized by disease-specific cohort. This summary will be presented by MedDRA primary SOC and PT.

6.2. Disposition of Participants

The number and percentage of participants who complete treatment, who are on treatment, who discontinue study drug with primary reason for discontinuation, who are on study, and who withdraw from the study with a primary reason for study withdrawal will be summarized for all participants in FAS by tumor type specific cohort. All participants with deviations to inclusion and/or exclusion criteria will be listed.

6.3. Protocol Deviations

Protocol deviations recorded in the eCRF will be presented in the participant data listings. Protocol deviations will be summarized descriptively.

6.4. Exposure

For participants in the safety evaluable population, exposure to INCMGA00012 will be summarized descriptively by disease-specific cohort separately as follows:

- **Total number of infusions:** Total number of infusions by participant with a nonzero dose of INCMGA00012.
- Total dose administered (mg): Sum of the cumulative actual dose that has been administered. Actual dose at each infusion is calculated as estimated volume delivered / prepared volume × 500 mg at each infusion.
- Average dose (mg): Total dose administered (mg) / total number of infusions.

- **Duration of treatment (days):** Date of last dose of INCMGA00012 date of first dose of INCMGA00012 + 1.
- **Dose modifications:** Number of participants who had dose delay or infusion interruption of INCMGA00012 and reason for infusion interruption will be summarized by disease-specific cohort.

6.5. Prior and Concomitant Medication

Prior medications and concomitant medications will be coded using the WHO Drug Dictionary and summarized by WHO drug class and WHO drug term. Results will be summarized as number and percentage of participants with prior and concomitant medications by WHO drug class in the FAS. For the summary of concomitant medication, only medications starting on or after the first dose of study drug and no later than 90 days after the last dose of INCMGA00012 will be included. Medications with missing start/end date will be considered as concomitant medications in summary. Other medications will be provided in the listing. Medications intended to manage irAEs as well as prophylaxis/premedication used to prevent infusion reactions may be summarized separately. Post-therapy and nondrug therapy will also be listed per CRF.

7. EFFICACY

Appendix A provides a list of planned tables, figures, and listings.

7.1. General Considerations

Efficacy endpoints of this study include ORR together with DCR, DOR, and PFS as determined by the investigator based on RECIST v1.1, and OS. Listings of response assessments at each visit will be provided. All efficacy analysis will be presented by disease-specific cohort

7.2. Efficacy Hypotheses

Not applicable.

7.3. Analysis of the Efficacy Parameters

The efficacy parameters will be analyzed using FAS.

7.3.1. Response Criteria

Overall disease status will be categorized using RECIST v1.1. Participants will have their overall response evaluated as CR, PR, SD, PD, or NE at each postbaseline radiological assessment based on changes in target lesions, nontarget lesions, and appearance of new lesions.

7.3.2. Primary Analysis

7.3.2.1. Overall Response Rate

The primary endpoint of the study is ORR, defined as the percentage of participants with CR or PR at any postbaseline visit before the first assessment of PD or new anticancer therapy, according to RECIST v1.1 (Eisenhauer et al 2009) as determined by the investigator. Participants who do not have sufficient baseline data to ascertain a response will be included in the denominators in the calculation of ORR. The analysis of ORR will be based on the FAS. Overall response rate and its exact 95% CI will be presented.

For participants with measurable disease at baseline, the RECIST v1.1 assessment criteria presented in Table 3 can be used to determine the overall response at a given timepoint based on the target lesion, nontarget lesion, and new lesion assessments.

Table 3:	RECIST	Evaluation	Criteria f	for Overall	Response
----------	--------	-------------------	------------	-------------	----------

Target Lesions	Nontarget Lesions	New Lesions	Overall Response
CR	CR	No	CR
CR	Non-CR/Non-PD	No	PR
CR	NE	No	PR
PR	Non-PD or NE	No	PR
SD	Non-PD or NE	No	SD
Not all evaluated	Non-PD	No	NE
PD	Any	Yes or No	PD
Any	PD	Yes or No	PD
Any	Any	Yes	PD

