12-lead ECG	Х					X	Either Fridericia or Bazett method of correction is acceptable for QT.
Efficacy assessments						•	·
Tumor imaging/response assessments	X			X*			* After efficacy analysis is complete, imaging to be performed per standard of care. Complete response or PR should be confirmed by imaging at least 4 weeks after initial documentation.
ECOG performance status	Х	Х	Х		Х		
Post study anticancer therapy status					X	X	
Survival status					Х	Х	

Table 3:Schedule of Activities (Continued)

	Screening		Treat	ment		Follow-Up	
Visit Day (Range)	28 Days	Cycle 1 Day 1	Cycle ≥ 2 Day 1 (± 3 d)	Q8W (± 7 d)	EOT ^a	28 Days After Last Dose (± 7 d)	Notes
Clinical laboratory assessments							
Serum chemistries	X	X*	Х			Х	* Not necessary on C1D1 if performed during screening within 7 days on C1D1.
Hematology	X	X*	Х			Х	* Not necessary on C1D1 if performed during screening within 7 days on C1D1.
Lipid panel (fasting)	X						
Coagulation panel	X						
Thyroid panel	X		X*			Х	* Every third cycle (C4, C7, C10, etc).
Urinalysis	X						
Pregnancy testing	X	X*	X		X**	X**	 * Not necessary on C1D1 if performed during screening within 7 days on C1D1. ** Can be performed at either EOT visit or 28 days after last dose. Timing and type of testing may be adjusted based on country-specific requirements.

a If EOT is ≥ 21 days postdose, the EOT visit will also serve as the 28-day follow-up visit. If EOT is < 21 days postdose, the 28-day follow-up visit is required.

Table 4	4: Ph	armacokinetic			Sample	Collect	tions				
			Cycle 1	Cycle 2 Day 1	Tre Cycle 4 Day 1	eatment P Cycle 6 Day 1	eriod Cycle 7 Day 1	Cycle 8 Day 1	Cycle 12 Day 1		
Sample	Collection	Purpose/Analysis	Day 1	$(\pm 3 d)$	$(\pm 3 d)$	$(\pm 3 d)$	$(\pm 3 d)$	$(\pm 3 d)$	$(\pm 3 d)$	ЕОТ	Notes
Serum	PK serum	РК	X*	X	X	X				Xª *	Samples will be collected preinfusion and 10 minutes postinfusion (± 10 minutes) on Day 1 of Cycles 1, 2, 4 and 6. * Additional PK samples will be collected 4 hours (± 15 minutes) postinfusion on Day 1 of Cycle 1 and at EOT.

^a A sample will be collected at the EOT visit or, if no separate EOT visit is performed, at the 28-day safety follow-up visit.

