2.2. Rationale for Study Design

The study is an open-label, nonrandomized, multi-cohort trial that is designed to provide proof of concept for INCMGA00012 in key indications where other PD-1 inhibitors have already shown efficacy. Clinical studies are an important mechanism for providing access to promising therapies where it may otherwise be limited (eg, due to labeling restrictions or insufficient reimbursement).

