8.2. Efficacy Assessments

Objective assessment of disease status will be evaluated according to RECIST v1.1 (Eisenhauer et al 2009) and entered into the eCRF. Efficacy assessments of response should be performed according to schedule found in Table 3. Scans should follow calendar days and should not be delayed for treatment holds or interruptions. Confirmation of CR or PR should be confirmed by imaging at least 4 weeks after initial documentation.

Participants who discontinue study treatment will not require further disease assessments.

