8.2.1. Tumor Imaging

Disease assessment and tumor response to study drug will be evaluated according to RECIST v1.1 guidelines (Eisenhauer et al 2009) as described in Appendix B. The recommended method for measuring and following tumor burden will be CT scan, which should be performed using consistent techniques and facilities. Alternative modalities such as MRI may be substituted for a CT scan at the discretion of the investigator, provided that the same modality is used throughout the study and the methodology is consistent with RECIST v1.1. Initial tumor imaging must be performed within 28 days before the first dose of study drug. Tumor lesions that are located in a previously irradiated area or in an area subjected to other loco regional therapy should not be selected as target lesions unless there has been demonstrated progression in the lesion. Additionally, it is recommended that tumor lesions selected for excisional biopsy not be selected as target lesions. After completion of the primary efficacy analysis, scans may be performed per the institutional standard of care. Only the overall assessment (eg, response category) by the investigator to support continuation of study drug will be collected in the EDC.

Computed tomography or MRI scan of the brain will be performed at screening if there are signs or symptoms suggesting that the participant has disease involvement in the CNS.

8.2.2. iRECIST

iRECIST is not used to determine efficacy of INCMGA00012 in this study but may be used for patient management with the decision to treat beyond conventional RECIST progression documented in the study file.

Immunotherapeutic agents may produce antitumor effects by potentiating endogenous cancer-specific immune responses. The response patterns seen with such an approach may extend beyond the typical time course of responses seen with cytotoxic agents and can manifest a clinical response after an initial increase in tumor burden or even the appearance of new lesions. iRECIST was developed to ensure a consistent methodology for assessing response to immunotherapy (Seymour et al 2017). The use of iRECIST accounts for potentially different response patterns of immunotherapies and includes a requirement for the confirmation of progression to rule out or confirm pseudoprogression, which should be performed between 4 and 8 weeks after the initial determination of iUPD.

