10.4.1.1. Overall Response Rate

The primary endpoint of the study is ORR, defined as the proportion of participants with an objective response (CR or PR), according to RECIST v1.1 (Eisenhauer et al 2009) as determined by the investigator. The primary analysis of ORR will be based on the FAS population as defined in Table 14 and will be performed once all participants on study treatment have been followed for at least 6 months from the start of treatment or prematurely discontinued study treatment. Overall response rate and its exact 95% CI will be presented. Overall response rate will not be recalculated after the primary analysis is performed.

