APPENDIX B. RESPONSE EVALUATION CRITERIA FOR SOLID TUMORS VERSION 1.1

Evaluation of Target Lesions

CR	Disappearance of all target lesions.
PR	At least a 30% decrease in the sum of the LD of target lesions, taking as reference the baseline sum LD.
PD	At least a 20% increase in the sum of the LD of target lesions, taking as reference the smallest sum LD recorded since the treatment started, and the sum must also demonstrate an absolute increase of at least 5 mm or the appearance of 1 or more new lesions.
SD	Neither sufficient shrinkage to qualify for PR nor sufficient increase to qualify for PD, taking as reference the smallest sum LD since the treatment started.

CR = complete response; LD = longest diameter; PD = progressive disease; PR = partial response; SD = stable disease.

Evaluation of Nontarget Lesions

CR	Disappearance of all nontarget lesions and normalization of tumor marker level.
Incomplete non-CR/ non-PD/SD	Persistence of 1 or more nontarget lesion(s) and/or maintenance of tumor marker level above the normal limits.
PD	Appearance of 1 or more new lesions and/or unequivocal progression of existing nontarget lesions. ^a

CR = complete response; PD = progressive disease; SD = stable disease.

^a Although a clear progression of "nontarget" lesions only is exceptional, in such circumstances, the opinion of the treating physician should prevail, and the progression status should be confirmed later on by the review panel (or study chair).

Evaluation of Best Overall Response

- The best overall response is the best response recorded from the start of the treatment until disease progression/recurrence (taking as reference for PD the smallest measurements recorded since the treatment started). In general, the participant's best response assignment will depend on the achievement of both measurement and confirmation criteria.
- Note: In nonrandomized studies where response is the primary endpoint, confirmation of PR or CR is needed to deem either one the 'best overall response'.

Target Lesions	Nontarget Lesions	New Lesions	Overall Response
CR	CR	No	CR
CR	Incomplete response/SD	No	PR
PR	Non-PD or NE	No	PR
SD	Non-PD or NE	No	SD
PD	Any	Yes or No	PD
Any	PD	Yes or No	PD
Any	Any	Yes	PD

CR = complete response; PD = progressive disease; PR = partial response; NE = not evaluable; SD = stable disease.

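### The primary responder is not settled: protocol Appendix B, Table 3 and 8.2 call for confirmed CR/PR, while the SAP and protocol 10.4.1 count a single CR or PR

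*SAP*

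**What the plan says.** **Texts that count a single CR or PR.** SAP 7.3.2.1 has ORR "defined as the percentage of participants with CR or PR at any postbaseline visit before the first assessment of PD or new anticancer therapy". SAP 7.3.2.2 takes the best response up to first PD; it sets a minimum of 7 weeks for SD and no condition on CR or PR. SAP Table 3 derives the response at one timepoint only. Protocol 10.4.1.1 has "ORR, defined as the proportion of participants with an objective response (CR or PR), according to RECIST v1.1", without mention of confirmation, and the first sentence of 10.4.1.2 counts a reported CR or PR that precedes other anticancer therapy.

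**Texts that call for confirmation.** Protocol Appendix B: "In nonrandomized studies where response is the primary endpoint, confirmation of PR or CR is needed to deem either one the" best overall response. Protocol Table 3: "Complete response or PR should be confirmed by imaging at least 4 weeks after initial documentation". Protocol 8.2 repeats this: "Confirmation of CR or PR should be confirmed by imaging at least 4 weeks after initial documentation". Protocol 2.2 shows that the Appendix B note applies: "The study is an open-label, nonrandomized, multi-cohort trial".

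**Texts that can be read either way.** Protocol 8.2.1 evaluates response by RECIST v1.1 "as described in Appendix B. The recommended method for measuring and following tumor burden will be CT scan". The second sentence of 10.4.1.2 makes a participant a nonresponder when later missing assessments prevent the endpoint from being evaluated; it names no confirmatory scan. SAP 10.1 declares no change from the protocol's analyses. The planned response table, 2.1.1 in SAP Appendix A, does not say in its title whether responses are confirmed; its shell is in a separate document.

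**The concern.** This is the primary endpoint of an open-label trial in which the investigator assesses response. There is no hypothesis test (protocol 10.3, SAP 3.4), so the estimate and its exact CI in each cohort are the whole primary result, and the numerator has to be unambiguous. An analyst who follows Appendix B and one who follows SAP 7.3.2.1 can both claim to follow the plan and still report different ORRs. The split lies within the protocol as well as between protocol and SAP, so the rule that one document prevails over the other would not settle it.

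DOR is affected too. SAP 7.3.3.1 starts it at the first objective response, so whether a single unconfirmed CR or PR counts decides who enters that analysis.

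**Working it through.** **1. The plan's own figures.** Protocol Table 13 and SAP Table 2 give exact 95% CIs for n = 30. The Clopper-Pearson limits for x responders of n are: lower = the 0.025 quantile of Beta(x, n − x + 1); upper = the 0.975 quantile of Beta(x + 1, n − x). All six rows reproduce to one decimal (x = 3, 5, 7, 9, 11, 12); for example, 12/30 gives 40.0% (22.7, 59.4). The table depends only on the count, so it fits either definition and does not show which one was meant.

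**2. Direction.** A confirmed response needs a CR or PR and then a second one, both before PD and before new anticancer therapy. The first of the two already satisfies SAP 7.3.2.1. With the same FAS denominator, cutoff, PD rule and new-therapy rule, confirmed responders are therefore a subset of SAP responders, and SAP ORR ≥ confirmed ORR.

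As a check, all sequences of 1 to 6 assessments over CR, PR, SD, PD and NE were enumerated: 5 + 25 + 125 + 625 + 3,125 + 15,625 = 19,530. Taking confirmation simply as a CR or PR at two assessments before first PD, none was a confirmed response without being a SAP response, and 4,740 were SAP responses without confirmation. These are counts of patterns, not probabilities.

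**3. Size.** The documents give no share of unconfirmed responses. One response is 1/30 = 3.3 points. For illustration, assume k = 0 to 3 unconfirmed, starting from 12/30 or 9/30 under the SAP rule:

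| k | From 12/30: ORR (exact 95% CI) | From 9/30: ORR (exact 95% CI) |
|---|---|---|
| 0 | 40.0% (22.7, 59.4) | 30.0% (14.7, 49.4) |
| 1 | 36.7% (19.9, 56.1) | 26.7% (12.3, 45.9) |
| 2 | 33.3% (17.3, 52.8) | 23.3% (9.9, 42.3) |
| 3 | 30.0% (14.7, 49.4) | 20.0% (7.7, 38.6) |

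The shift is 0 to 3/30 = 10.0 points. CI widths run from 38.6 − 7.7 = 30.9 points (6/30) to 59.4 − 22.7 = 36.7 points (12/30).

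**4. Whether the schedule can supply confirmation.** Protocol Table 3 images every 8 weeks ± 7 days. Consecutive on-schedule scans are at least 56 − 7 − 7 = 42 days apart, which exceeds the 28 days needed. For a participant who stays on treatment, the next routine scan can serve as the confirmatory one.

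**The case against.** **Import by reference.** SAP 7.3.2.1 works according to RECIST v1.1, protocol 8.2.1 points to Appendix B, and SAP 10.1 declares no departure. On that reading confirmation is already in the plan and the SAP is merely silent. The reading is available, but the SAP's wording is a complete counting rule that one CR or PR at any visit satisfies. The protocol also says confirmed where it means it: the Phase 1 responses in 2.1.1 and the CR rule in 4.1. Two tenable readings of a primary endpoint are the problem itself.

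**Scheduling language.** Table 3 and 8.2 say only that imaging should confirm a response; they do not define who counts. That is fair. Appendix B does the classifying, and it does so for best overall response, whereas SAP 7.3.2.1 does not define ORR through BOR.

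**Agreement of the statistical sections.** If nothing is imported, protocol 10.4.1.1, the first sentence of 10.4.1.2 and SAP 7.3.2 agree on a single CR or PR, so making confirmed the primary is partly a choice. It is, but it is the choice that Appendix B makes for this design, and the other rate is kept.

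**Small stakes.** The study is signal-finding and untested, and the illustrated shift lies well inside the CI. This limits the consequence; it does not settle which number is the primary result.

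**Timing and cost.** The Amendment 4 rationale (November 2020) reports the 6-month follow-up condition as met, and protocol 10.4.1.1 bars recalculating ORR afterwards. A redefinition may therefore be post hoc. In addition, a first response at the week-24 scan would next be imaged at about week 32, so it could be pending at a 6-month cutoff without having failed confirmation. Both points stand and shape the fix.

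**Conclusion.** The concern holds. The documents give two definitions of the primary responder, and the SAP, followed literally, gives an ORR equal to or above the confirmed one. The direction is certain given the same FAS, cutoff, PD rule and new-therapy rule. The size is not known: it may be zero, and each unconfirmed response moves a cohort of 30 by 3.3 points. The 0 to 10.0 point range rests wholly on the assumed 0 to 3 unconfirmed responses. The effect is on the reported ORR, its CI and membership of the DOR analysis; no test result depends on it.

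**What to change.** **SAP 7.3.2.1 and 7.3.2.2**
- Define the primary responder as a CR or PR confirmed by a second CR or PR at least 4 weeks later, before PD and before new anticancer therapy.
- Count a response with no confirmatory scan by the data cutoff as a nonresponder in the primary ORR. This is consistent with the second sentence of protocol 10.4.1.2.
- Show the number of such responses by cohort and reason, separating treatment stopped, scan not yet due and scan missed.
- State how an unconfirmed CR or PR enters BOR. One option, found in neither document, is SD if the 7-week minimum is met, and otherwise PD or NE by the next assessment.

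**Linked items**
- Use the same responder set for DOR, timed from the first of the two assessments.
- Report the unconfirmed ORR as supportive and label both rates in Table 2.1.1.
- Align protocol 10.4.1.1 and 10.4.1.2, or list the rule in SAP 10.1 if the protocol is not amended.

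**If the primary analysis has already been done,** report both rates and label which was prespecified. The two documents do not settle that, so the label should rest on dated records such as the table shells. A later change of definition must be identified as one.

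**Cost.** SAP wording and one supportive row; no new scans. A protocol amendment may need IRB/IEC approval if it counts as a design change (protocol 11.1). The primary ORR may be lower, and some of that will not reflect failed confirmation: responses first seen near the cutoff may still be pending, and early stoppers may lack a second scan because "Participants who discontinue study treatment will not require further disease assessments". The supportive rate and the count by reason make this visible but do not remove it.
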